Kaplan-Meier estimates (product-limit estimates) for the time to first moderate/severe flare will also be provided by study intervention group together with a summary of associated statistics (median, Q1 and Q3, minimum and maximum) including the corresponding two-sided 95% CI of the median (calculated according to Brookmeyer and Crowley). Rates of participants with moderate/severe BILAG flare together with their 95% CI (using the log-log transformation according to Kalbfleisch and Prentice) will be provided at each on-treatment scheduled visit. The estimate of the standard error will be computed using Greenwood's formula. In addition, the number of participants with at least one event (overall and by flare severity) will be presented.

Cumulative distribution function estimated using Kaplan-Meier method will be displayed by study intervention group.

14.3.12 Time to First SFI Severe Flare from Day 1 through Week 24

Attributes of the estimand are described in the table below. It will be produced for the final analysis.

Endpoint Time to first SFI severe flare from Day 1 through Week 24	
--	--

CONFIDENTIAL INFORMATION

Population(s)	SLE participants from Cohort B
Treatment	Enpatoran vs placebo
Population-level	Hazard ratio (conditional on stratification factors) between each active dose and placebo
summary measure	

CCI

Mild or moderate flare is defined as meeting any of the criteria below:

- Change in \mathbb{CC} score ≥ 3 (but no more than 12)
- New or worsening disease activity in:

o CC

- Nasopharyngeal ulcers AND/OR
- o Pleuritis AND/OR
- o Pericarditis AND/OR
- o Arthritis AND/OR
- o Fever (SLE)
- Increase in prednisone, but not to > 0.5 mg/kg/day
- Added NSAID or hydroxychloroquine for SLE activity
- ≥ 1.0 increase in PGA score, but not to more than 2.5

Severe flare is defined as meeting any of the criteria below:

- Change in CCI score > 12
- New or worsening disease activity in:

- Nephritis AND/OR
- o Myositis AND/OR
- o Platelets < 60,000 AND/OR
- o Hemolytic anemia: Hb < 70 g/L or decrease in Hb > 30 g/L
- Increase in prednisone to > 0.5 mg/kg/day for any kind of flare
- New cyclophosphamide, azathioprine, methotrexate for SLE activity

- Hospitalization for SLE activity
- Increase in PGA score to > 2.5

Since some laboratory components of the CC	will be blinded during the study, the
eCRF item related to the change in CC	cannot be used. Hence, change in CC
will be derived using the actual total score	
instrument score of 3 points or more [but not to more to	
instrument score to greater than 12' in eCRF will not	_

Time to first SFI severe flare (weeks) will be derived as follows:

Time to first SFI severe flare = $[min(Dates \ of \ visit \ with \ SFI \ severe \ flare) - Date \ of \ randomization + 1]/7$

The following censoring rules will be applied:

- Participants discontinuing the study prior to Week 24 without SFI severe flare will have their time to first SFI severe flare censored at the last visit at which flare could have been assessed (i.e., date of last SFI assessment). Participants discontinuing the study prior to any post-baseline assessments will be censored at randomization date.
- Participants completing the 24-week treatment period without SFI severe flare will have their time to first moderate/severe flare censored at Week 24.

The same analysis as described for time to first moderate/severe BILAG flare (section 14.3.11) will be performed.

14.3.13 Change from Baseline in Skindex-29+3 Scores at Week 24

Attributes of the estimands related to Skindex-29+3 domain scores are described in the table below.

	Change from Baseline in Skindex-29+3 symptom domain score at Week 24		
	Change from Baseline in Skindex-29+3 functioning domain score at Week 24		
Endpoint(s) • Change from Baseline in Skindex-29+3 emotion domain score at Week 24			
	Change from Baseline in Skindex-29+3 lupus-specific domain score at Week 24		
	Participants with a baseline Skindex-29+3 and at least one post-baseline Skindex-29+3		
	score in:		
Population(s)	Cohort A		
	 Cohort B with CLASI-A ≥ 8 at Screening and confirmed at Day 1 		
	Enpatoran vs placebo		
Treatment			
Population-level	Model LS mean difference between study intervention groups		
summary measure			

Descriptive Analysis

Symptom, functioning, emotion domain scores and their changes from Baseline will be summarized using descriptive statistics at Baseline and each on-treatment scheduled visit.

A boxplot displaying the raw score by scheduled visit will be provided for each domain.

Inferential Analysis

For each scale, an MMRM as described in section 14.3.9 will be fitted. It will include the change in score from baseline as the dependent variable, study intervention group, analysis visit, treatment by analysis visit interaction as categorical variables, stratification factors (see Section 14), and baseline score as a continuous variable will be fitted. The model will include data until Week 24 visit.

LS means for change from Baseline in each score together with its 95% CIs will be presented by study intervention group and analysis visit, in a tabular and graphical form. The difference in the LS means between each study intervention group and placebo together with accompanying two-sided 95% CI will also be tabulated.

Empirical cumulative distribution function (eCDF) for Week 24 change from Baseline will be displayed by study intervention group to depict the treatment effect across the population.

[figure not shown]
14.3.14 Change from Baseline in FACIT-Fatigue Score at Week 24

[figure not shown]
Attributes of the estimand are described in the table below.

[figure not shown]
Endpoint	Change from Baseline in FACIT-Fatigue score at Week 24		
Population(s)	Participants with a baseline FACIT-Fatigue score and at least one post-baseline FACIT-Fatigue score in: Cohort A Cohort B		
Treatment	Enpatoran vs placebo		
Population-level summary measure	Model LS mean difference between study intervention groups		

The same analysis as described for change from Baseline in Skindex-29+3 scores (see section 14.3.13) will be conducted (same outputs will be provided).

[figure not shown]

[figure not shown]

[figure not shown]

[figure not shown]
Version 4.0

15 Safety Analyses

Safety analyses will be performed according to the as-treated principle on the safety analysis set by cohort and study intervention group unless otherwise specified. These will be conducted at final analyses of Cohort A and Cohort B. The analyses planned for the primary analysis of Cohort A are identified with an asterisk (*).

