BILAG Flare

Use of the BILAG index for evaluating flares has been identified as a meaningful way of evaluating the efficacy of drugs; this judgment has been corroborated by external advisors and regulatory authorities.

BILAG assessments should be conducted by a trained evaluator.

The BILAG index flare definition were used in the SLICC Flare study in May 2009 published in Annals of Rheumatic Diseases (Isenberg 2011).

On the participant level:

- 1. A severe flare is defined as at least one BILAG A score in any organ systems due to one or more items that are new or worse*, in the month leading up to the current visit, compared to the patient's condition during the previous month
- 2. A moderate flare is defined as at least 2 BILAG B organ scores due to items that are new or worse* in the moth leading up to the current visit previous month, when the participant does not meet the criteria for the severe flare
- 3. A mild flare is defined as one single BILAG B score in any organ systems due to items that are new or worse* in the month leading up to the current visit, compared to previous month, or at least 3 BILAG C scores in any organ systems due to items that are new or worse
- 4. No flare is defined as without meeting any of these criteria.

Investigators will be trained to score worse only if there is significant deterioration compared to the prior month and to score new only when the item was not present in the prior month according to the BILAG glossary. In organs (renal and hematological) in which an A, B, or C score depend on whether or not laboratory results are attributed to SLE, Investigators will be queried to ensure that there is medical justification for this decision.

A copy of the BILAG 2004 and glossary is provided in the Investigator portal.

SLEDAI Flare Index

The SFI can be used with any version of the SLEDAI and will be used with the CCI for the purposes of this trial.

[figure not shown]
A mild/moderate flare is defined as any of the following:

•	Increase in SLEDAI instrument score of	of 3 po	oints or more ((but total	score not to	more than	12)
---	--	---------	-----------------	------------	--------------	-----------	-----

A severe flare is defined as any of the following:

• Increase in SLEDAI instrument score leading to total score > 12.

[figure not shown]
^{*}On the organ system level:

Patient-Reported Assessments

Functional Assessment of Chronic Illness Therapy-Fatigue

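### SAP 14.3.12 defines the SLEDAI part of an SFI severe flare as a change above 12; the protocol defines it as a rise to a total above 12

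*SAP*

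**What the plan says.** Protocol Appendix 8, under the SLEDAI Flare Index, gives the SLEDAI component of a severe flare as "Increase in SLEDAI instrument score leading to total score > 12". Its mild/moderate counterpart is a rise of at least 3 points, with the total score capped at 12. Both protocol lines therefore turn on the level reached.

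SAP 14.3.12 gives the severe component as "Change in CCI score > 12". The mild/moderate component is a change of at least 3, qualified by "but no more than 12", without saying whether 12 limits the change or the total.

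The neighbouring criteria in the same SAP lists are worded as levels: "Increase in PGA score to > 2.5" and "Increase in prednisone to > 0.5 mg/kg/day for any kind of flare" for severe, and "increase in PGA score, but not to more than 2.5" for mild/moderate. The SAP also cites the eCRF item for the severe component, worded as "instrument score to greater than 12". It says this item cannot be used, because some laboratory parts of the score are blinded during the study, and that the change "will be derived using the actual total score". The sentence giving that derivation is broken in the available text.

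Protocol 9.4 says that analysis changes not needing an amendment are described in the IAP and the CSR. SAP Section 7 lists only the change to the FAS definition.

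**The concern.** A rise that takes the score above 12 is a much weaker requirement than a rise of more than 12 points. Protocol 4.1 gives SLEDAI of at least 6 as one of two alternative disease-activity criteria for Cohort B, so reference scores well above zero are to be expected, and there the two rules separate widely.

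The criterion line matters more than usual here. The SAP sets the eCRF item aside and derives this component by program, so the protocol-consistent wording on the form does not protect the endpoint. A programmer who follows the SAP line would count fewer severe flares on this component, or count them at a later visit. That would feed into the hazard ratios, confidence intervals and Kaplan-Meier curves for a named secondary endpoint.

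The mild/moderate line adds a second problem. Depending on what the cap of 12 refers to, the missed cases are either graded mild/moderate or fall in neither tier on this component.

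**Working it through.** The plan gives no figure to reproduce, so the check compares the two rules directly. Let r be the reference score and d the rise, both integers, with r from 0 to 12 and d at least 1.

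- Protocol severe: r + d > 12.
- SAP severe, read literally: d > 12.

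If d > 12, then r + d > 12 for any r of 0 or more, so every SAP-severe case is also protocol-severe. The reverse fails when 13 − r ≤ d ≤ 12. The missed totals then run from 13 to r + 12, which is (r + 12) − 13 + 1 = r values. The lowest severe total is 13 under the protocol and r + 13 under the SAP.

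The mild/moderate line has two possible readings:

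- Cap on the change: 3 ≤ d ≤ 12.
- Cap on the total, as in the protocol: d ≥ 3 and r + d ≤ 12.

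| r | Lowest severe total, protocol | Lowest severe total, SAP | Missed totals | Graded mild/moderate if 12 caps the change | Graded mild/moderate if 12 caps the total |
|---|---|---|---|---|---|
| 0 | 13 | 13 | none | – | – |
| 6 | 13 | 19 | 13–18 (6 values) | 6 of 6 | 0 of 6 |
| 10 | 13 | 23 | 13–22 (10 values) | 10 of 10 | 0 of 10 |
| 12 | 13 | 25 | 13–24 (12 values) | 10 of 12 | 0 of 12 |

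At r = 12, rises of 1 and 2 points are severe under the protocol. Under the SAP they are in neither tier on this component, even if 12 caps the change. If 12 caps the total, no missed case is mild/moderate, because every missed total is at least 13.

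As an example, a rise from 10 to 14 is severe under the protocol (14 > 12). Under the SAP line it is a change of 4 and not severe. For r = 10 to 12, the protocol makes every rise of 3 or more severe on this component, since r + 3 is already at least 13.

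The values of r are illustrations. The counts are of possible totals, not of participants or events.

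**The case against.** The strongest reply is that the SAP line is loose shorthand. The surviving eCRF wording has the level form, the stated reason for dropping that item is blinding and not a new threshold, and the mild/moderate line looks like a compression of the protocol's wording. The unreadable part of the derivation sentence may state the comparison correctly. It is also an inference that the redaction hides only the instrument name. Silence in SAP Section 7 proves little, because an author who believed the definition was merely being transcribed would declare nothing.

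Much of this is fair as to intent. It does not repair the text: no readable sentence corrects the criterion lines, and the neighbouring PGA and prednisone criteria show that the SAP writes a level when it means one. A shorthand that reads as a different rule still needs correcting when the component is derived by program.

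The limits on consequence also stand. A severe flare requires any one of several criteria, including organ involvement, low platelets, haemolytic anaemia, a prednisone increase, a new immunosuppressant, hospitalization or PGA above 2.5. Some missed cases would be captured that way, and the net loss of events could be small.

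**Conclusion.** The concern holds. As written, the SLEDAI component in SAP 14.3.12 is a strict subset of the protocol's, and the mild/moderate cap is ambiguous. For reference scores up to 12 the threshold for a severe flare on this component moves from 13 to r + 13, and the rules agree only at r = 0.

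This rests on integer scores, on the redacted word being the instrument name, and on literal coding of the criterion line. Whether a different rule was intended cannot be told from the documents.

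The effect is confined to one component of a Cohort B secondary endpoint. Its p-values are nominal (protocol 9.4) or exploratory (SAP 14.3.11, whose analysis 14.3.12 reuses). No primary test is affected. It should be fixed before final programming.

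**What to change.** Restate the two SLEDAI lines in SAP 14.3.12 to match Appendix 8:

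- Severe: score increased and total above 12.
- Mild/moderate: increase of at least 3 with total not above 12.

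If a change above 12 points is really intended, declare and justify it in SAP Section 7. While restating, confirm which reference visit the increase is measured from. The derivation sentence is not fully readable here, so no omission is claimed on that point.

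The cost is two lines of wording and a small programming check. No new data are needed, because the SAP already derives this component from the actual total scores.

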15.1 Adverse Events

Treatment-emergent adverse events (TEAE) are those events with onset or worsening dates occurring on or after the first dose of study intervention.

This also includes AEs ongoing at Baseline, which first improve under study intervention and then worsen irrespective of baseline. Adverse events with changes in toxicity grade, seriousness or outcome of AEs are recorded as separate entries in the eCRF with associated end and start dates (start date equals end date of previous entry, supported in eCRF v8.4 by "AECHGID" in SUPPAE). Records of the same AE will be considered as one event in the analysis. If the severity or seriousness of the reported event worsens after start of treatment, the TEAE flag will be re-evaluated for the worse and the subsequent records as per the TEAE definition. These events will be kept as separate records in the database in order to maintain the full detailed history of the events. The overall outcome of the adverse event is the outcome of the last event in the sequence. When such AEs are listed, start, end date and outcome should be provided together with change date, toxicity grade and seriousness per episode.

Adverse events are considered as related to study intervention if their relationship with the study intervention is missing, unknown or yes.

Adverse events will be summarized using the latest version of MedDRA at the time of the database lock with PT as event category and MedDRA primary SOC body term as body system category.

Analysis by severity will be performed according to NCI-CTCAE version 5.0. In case a participant has events with missing and non-missing grades, the maximum of the non-missing grades will be used. No imputation of missing grades will be performed.

Incomplete AE-related dates will be handled as specified in section 9.10.

All analyses described in this section 15.1 will be based on TEAEs if not otherwise specified.

Unless otherwise specified, TEAEs will be summarized by number and percentage of participants with at least one TEAE in the category of interest, by study intervention group, primary SOC in alphabetical order, and PT in decreasing incidence overall.

CONFIDENTIAL INFORMATION

88/125

Each participant will be counted only once within each SOC or PT. If a participant experiences more than one AE within a SOC or PT for the same summary period, only the AE with the strongest relationship or the worst severity, as appropriate, will be included in the summaries of relationship and severity.

The 3-tier approach to AE reporting will be applied.

15.1.1 All Adverse Events

Description of the Three-tier Analysis Approach

The 3-tier approach for summarizing and analyzing AEs in clinical studies will be followed. AEs in different tiers are analyzed using different types of statistical analysis.

Pre-specified AESI will be analyzed as part of Tier 1 if they fulfill the rule-of-4 (at least 4 participants in any of the study intervention groups). Otherwise, such AEs will be included in Tier 3. The pre-specified terms considered for Tier 1 are (see section 15.2.3 for further details):

•	Severe infections NCI-CTCAE grade ≥ 3 and all-related F	PTs

All of these prespecified events will be summarized in a table. Incidence rate and difference in incidence rate between each active group and placebo will be provided. A 95% CI for the difference in incidence rate will be provided for prespecified events fulfilling the rule-of-4 only. CI will be estimated using Miettinen & Nurminen method.

All TEAEs (unique preferred terms) will be classified as belonging to Tier 2 or Tier 3 and summarized in a table. Incidence rate and difference in incidence rate between each active group and placebo will be provided. A 95% CI for the difference in incidence rate will be provided for adverse events fulfilling the rule-of-4 only. CI will be estimated using Miettinen & Nurminen method.

Only TEAEs with at least one study intervention group with incidence proportion \geq 5% will be presented in the body of the CSR.

Statistical Outputs

The following tables will be provided:

- Overview of TEAEs including (*):
 - o TEAEs
 - o TEAEs, Grade ≥ 2 , Grade ≥ 3 , Grade ≥ 4
 - o Related TEAEs

- o Related TEAEs, Grade ≥ 2 , Grade ≥ 3 , Grade ≥ 4
- Serious TEAEs
- Non-serious TEAEs
- Related Serious TEAEs
- o TEAEs leading to death
- o Related TEAEs leading to death
- Prespecified Tier 1/3 TEAEs (displayed by term including incidences, risk differences and respective confidence limits for the difference in group incidence proportions, as applicable according to rule-of-4) as described above per the 3-tier analysis approach (see description of the 3-tier approach above)
- Tier 2 and Tier 3 TEAEs (displayed by PT including incidences, risk differences and respective confidence limits for the difference in group incidence proportions, as applicable according to Rule-of-4) as described above in the 3-tier analysis approach (see description of the 3-tier approach above)
- TEAEs by SOC and PT (*)
- TEAEs by SOC and PT and worst grade (Any Grade, Grade \geq 2, Grade \geq 3, Grade \geq 4) (*)
- Related TEAEs by SOC and PT (*)
- TEAEs excluding SAEs, with frequency $\geq 5\%$ in any study intervention group by SOC and PT. "Number of subjects with at least one event" represents the number of participants with at least one AE among AEs where frequency is $\geq 5\%$ in at least one study intervention group.

For Tier 1 and Tier 2 events each, a forest plot displaying incidence rates, differences in incidence rates as well as the CI for the difference will be provided.

The overview of TEAEs will also be provided in the population of CLE participants from Cohort A.

A listing of all AEs will be provided.

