2.3.5 Overall Benefit: Risk Conclusion

Considering the measures taken to minimize risk to participants in this study, the contemplated potential risks in association with enpatoran are justified by the anticipated benefits that may be afforded to participants with SLE or CLE.

3 Objectives and Estimands

Objectives	Estimand attributes	
Primary		
To evaluate the dose-response relationship of enpatoran in reducing disease activity based on CLASI-A	Endpoint: Percent change from Baseline in CLASI-A at Week 16 Population: Patients with active SCLE, DLE, or SLE with predominantly active lupus rash Note: Cohort A participants Treatment: Enpatoran vs placebo CCI Population-Level Summary: LS means (SE) as estimated by MMRM. The MCP-Mod procedure will be performed to evaluate the dose-response relationship.	
To evaluate the dose- response relationship of enpatoran in reducing disease activity based on BICLA response rate	Endpoint: BICLA response at Week 24 Population: Patients with active SLE Note: Cohort B participants Treatment: Enpatoran vs placebo Col Population-Level Summary: Responder rates and 95% CI. The MCP-Mod procedure will be performed to evaluate the dose-response relationship	

[figure not shown]
Objectives	Estimand attributes	
Secondary		
To evaluate the safety and tolerability of enpatoran compared to placebo	Endpoints: From Day 1 to the end of Safety Follow-up period Occurrence of TEAEs, SAEs, and AESI Occurrence of abnormalities (Grade 3) in laboratory parameters Occurrence of Clinically Important increases in QT Interval Corrected Using Fridericia's Formula (QTcF)	
To evaluate the efficacy in disease control of enpatoran compared to placebo in lupus participants with active lupus rash	 Endpoints: Change from Baseline in CLA-IGA at Week 16 and Week 24 Change from Baseline in Physician's Global Assessment of Cutaneous Lupus Disease Activity at Week 16 and 24 Population: Patients with active SCLE, DLE, or SLE with active lupus rash Note: Active SCLE, DLE and SLE participants from Cohort A OR Cohort B with CLASI-A ≥ 8 at Screening and confirmed at Day 1 	
	Population-Level Summary: LS mean (SE) at each visit and treatment difference (95% CI) as estimated by MMRM	

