15.2.3 Other Significant Adverse Events

The following events are defined as AE of Special Interest (AESI) as per protocol and will be included in Tier 1:

• Severe infections NCI-CTCAE grade ≥ 3

AESI will be identified using the corresponding flag entered in the "Adverse Event" eCRF page. In order to define the category to which they belong, SMQs or primary SOC will be used depending on the AESI (see table below).

Details of derivation for AESI categories are explained below:

AESI categories	Derivation
Severe infections	Primary SOC = 'Infections and Infestations' - Severe events only (i.e., ≥ Grade 3)
CCI	

AESI will be summarized as part of the 3-tier approach described in section 15.1.1 at primary analysis of Cohort A and final analyses of Cohort B.

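### The confidence interval for a pre-specified AESI is shown only once 4 participants in one arm have the event, so in Cohort A it is likely to be missing when AESI rates are low

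*SAP*

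**What the plan says.** Protocol Section 3 lists safety against placebo among the secondary objectives: "To evaluate the safety and tolerability of enpatoran compared to placebo". Its endpoints are TEAEs, SAEs and AESIs, together with Grade 3 laboratory abnormalities and QTcF increases. Protocol 9.4.2.1 adopts a three-tier approach to adverse events and leaves the details to the analysis plan.

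SAP 15.1.1 makes Tier 1 membership depend on the rule-of-4, which is met when at least 4 participants in any one study intervention group have the event. If it is not met, "Otherwise, such AEs will be included in Tier 3". For all pre-specified events, "Incidence rate and difference in incidence rate between each active group and placebo will be provided". The interval is conditional: "A 95% CI for the difference in incidence rate will be provided for prespecified events fulfilling the rule-of-4 only". On the method, "CI will be estimated using Miettinen & Nurminen method". Forest plots are planned for Tiers 1 and 2 only.

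SAP 15.2.3 attaches no condition: "The following events are defined as AE of Special Interest (AESI) as per protocol and will be included in Tier 1". It then refers back to 15.1.1 for how AESIs are summarised, including at the Cohort A primary analysis.

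**The concern.** A count threshold is a sensible filter for the long list of unselected preferred terms, where it separates Tier 2 from Tier 3. It suits a short list named in advance less well, because the point of naming those events is that their analysis should not depend on what is observed. Here the observed count decides the tier, whether an interval is printed and whether the event appears in a forest plot.

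What is lost is precision information at low counts. In an arm of 25, few or no events are compatible with a sizeable true excess. A point difference alone, which is simply zero when nobody has the event, does not show that. The two SAP sections also give different tier assignments for an AESI with fewer than 4 participants in every group.

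**Working it through.** The documents state no AESI rate, precision or detectable-difference figure, so there is no planned figure to reproduce. The event rates below are assumptions.

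**Inputs**
- Cohort A: about 100 participants randomised 1:1:1:1, so 25 per arm (Protocol 4.1).
- Safety is analysed for each cohort separately (Protocol 9.4.2).
- Trigger: at least 4 participants in any one group, placebo included (SAP 15.1.1). 4/25 = 16%.
- Interval: two-sided 95% (SAP Section 9), Miettinen-Nurminen (SAP 15.1.1).

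**How often the interval would be shown in Cohort A**

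For one arm, t(p) = P(Bin(25, p) ≥ 4). For the trial, P(shown) = 1 − the product over four arms of (1 − t).

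Same true rate in all four arms:

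| Rate | t(p), one arm | P(shown) |
|---|---|---|
| 2% | 0.0014 | 0.6% |
| 5% | 0.0341 | 13.0% |
| 8% | 0.1351 | 44.0% |
| 10% | 0.2364 | 66.0% |
| 12% | 0.3525 | 82.4% |

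For example, at 10%: 1 − (1 − 0.2364)^4 = 0.660. P(shown) reaches 50% at a common rate of about 8.5%.

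One arm raised, the other three at 2%:

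| Raised arm | P(shown) |
|---|---|
| 5% | 3.8% |
| 8% | 13.9% |
| 10% | 24.0% |
| 12% | 35.5% |
| 15% | 53.1% |

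For example, at 10%: 1 − (1 − 0.2364)(1 − 0.0014)^3 = 0.240. The 50% point is just under 15%.

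**What is left out**

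For 0/25 vs 0/25 the Miettinen-Nurminen limit has a closed form. With the variance factor N/(N−1) = 50/49, let k = 1.96² × 50/49 = 3.92. The limit is k/(25 + k) = 3.92/28.92 = 0.136, or 13.6 points in either direction. The other limits were solved numerically by restricted maximum likelihood.

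| Active vs placebo | Difference (points) | 95% CI (points) | Interval shown if no other arm reaches 4? |
|---|---|---|---|
| 0/25 vs 0/25 | 0 | -13.6 to +13.6 | No |
| 1/25 vs 0/25 | +4 | -9.8 to +19.8 | No |
| 2/25 vs 0/25 | +8 | -6.1 to +25.2 | No |
| 3/25 vs 0/25 | +12 | -2.4 to +30.2 | No |
| 4/25 vs 0/25 | +16 | +1.4 to +34.9 | Yes |

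The named method gives a finite interval at every count that the rule leaves out, including zero events, so nothing technical requires the restriction.

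**The case against.** The strongest reply is that this is a deliberate, pre-specified reporting convention. The protocol commits to three tiers and leaves the detail to the SAP. Incidence and the difference from placebo are always tabulated, and adverse events are listed, so anyone can compute the interval. That stands: the interval is unreported, not unobtainable.

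The conflict between sections can also be read narrowly, since 15.2.3 points to 15.1.1 and a planned output in 15.1.1 covers pre-specified events in Tier 1 or Tier 3. The operative rule can therefore be inferred, but the unconditional sentence in 15.2.3 still needs to agree with it.

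A reader might infer more than the documents support:
- **That this is the main safety comparison.** AESI occurrence is one of several secondary safety endpoints, and none is ranked above the others.
- **That the interval will usually be missing.** This depends on rates not given, and other AESI terms are blacked out. With all three doses at 10% and placebo at 2%, the interval is shown in 1 − (0.7636)^3 × 0.9986 = 55.5% of trials.
- **That a Cohort A signal is hidden.** It is not: 3/25 vs 0/25 has a score z of 1.77, below 1.96.
- **That Cohort B loses much.** Pooling both parts without dose adaptation (70 on a low dose, 90 on placebo), 3/70 vs 0/90 does give an interval just above zero (+0.1 to +11.9). At 4% vs 1%, applying the rule to those two arms alone cuts the chance of showing such an interval from 27.5% to 18.3%. But the trigger counts any group; with the other two doses also at 4% the chance is 25.2%.
- **That a p-value is withheld.** SAP 15.1.1 plans none at any count.

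**Conclusion.** The point holds as a low-severity reporting gap. In Cohort A, the interval is more likely than not to be omitted if the AESI rate is common to all arms and below about 8.5%, or if one arm is raised to less than about 15% with 2% elsewhere. Above those rates it is more likely to be shown.

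The low range is plausible for the one AESI that is visible, severe infection. Protocol Table 2 reports no clinical experience of it across the enpatoran studies, and Protocol 8.3.7 restricts AESIs to events deemed related. Neither statement gives a rate, so the probabilities remain conditional on the assumed values and on 25 treated participants per arm.

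The width of the intervals comes from the sample size and not from the rule. The rule's effect is that this width goes unreported when events are few. Separately from any assumed rate, SAP 15.1.1 and 15.2.3 should state the same tier assignment.

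**What to change.** In SAP 15.1.1, remove the rule-of-4 for the pre-specified AESIs. Keep them in Tier 1 whatever the count, in line with 15.2.3, and always report the risk difference with its two-sided 95% Miettinen-Nurminen interval for each dose vs placebo, including at 0 to 3 events. Keep the rule-of-4 only to separate Tier 2 from Tier 3. Rename the planned pre-specified output so that it no longer refers to Tier 3.

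The cost is one or two sentences of SAP text and a few more cells in a table already planned. The downside is that intervals at low counts will be wide.
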